1.2 Visit windows and retention definitions

Visit windows for the study visits were as follows:

- Screening + results visits: the entire screening process should not have taken longer than 6 weeks
- Enrolment visit: maximum of 3 days after completion of oral metronidazole treatment
- Day 7: Day 5 Day 9
- Month 1: ± 7 days
- Month 2: ± 7 days
- Month 6: ± 7 days

The following retention definitions were used:

- Early withdrawal: The participant informed a RU staff member that she no longer wants to participate in the study.
- Late visit: The participant did attend a study visit but after the visit window had closed.
- Skipped visit: The participant did not attend a study visit but did return to the study clinic for a subsequent study visit.
- Lost-to-follow-up: RU does not label a participant as lost to follow-up until study close-out. A participant is considered lost to follow-up at study close-out when multiple contact attempts by RU staff failed (as specified in the RU SOP for Retention) and the participant did also not return to the study clinic spontaneously before study close-out.
- Missed visit: All visits that should have taken place according to the study protocol but did not. This includes all study visits after an early withdrawal or after the last study visit made by a participant who is lost to follow-up, as well as all skipped visits.

2. Primary and secondary clinical endpoints

The endpoints of the study discussed in this SAP are:

Primary clinical objectives	Endpoints
1. To determine the safety of the	- Self-reported solicited and unsolicited (serious) adverse events
three biomedical interventions	(AEs) and social harms
compared to the control group.	 Clinician-observed speculum exam findings
2. To determine the preliminary	– BV by Amsel criteria, Nugent score 4-10* (versus 0-3), TV by
efficacy of the three biomedical	culture and symptomatic vaginal candidiasis at any time during
interventions compared to the	the intervention (Day 7, Month 1, Month 2)
control group in reducing BV	– BV by Amsel criteria, Nugent score 4-10* (versus 0-3), TV by
recurrence without increasing	culture, and symptomatic vaginal candidiasis after cessation of
vaginal candidiasis incidence.	the intervention (Month 6)
	* Abnormal Nugent scores will also be analysed as Nugent score
	7-10 versus 0-6.
Secondary clinical objectives	Endpoints
2. To determine preliminary	- Incidence of the following STIs between screening and Month
efficacy of the three biomedical	6: HIV, HSV-2, syphilis, CT and NG
interventions compared to the	 Incidence of UTI between screening and Month 6
control group in reducing the	
incidence of STIs and UTI.	

3. Participant flow

3.1 Retention (see also the flow diagram in Figure 1 above)

	N
Number of women who attended a Screening visit	176
Number of women who attended an Enrolment visit	74
Number of women who were randomised	68
Number of women who attended D7, M1, M2, and M6 visits	66, 67, 66, 64
Number of women who completed all scheduled study visits	60
Number of women who missed visits after randomisation	8
Number of women who withdrew early	4
Number of women who were lost-to-follow-up	0
Number of deaths	0
Number of completed study visits by randomised women, including the Enrolment visit	324
Number of skipped visits after randomisation	4
Number of missed visits after randomisation	12
Total person-months of data collected after randomisation	TBD
Total person-days of data collected after randomisation	TBD

3.3 Reasons for ineligibility during the screening process and at enrolment

During the screening process	N
HIV positive	
Pregnant	
Not at high risk of HIV/STIs/BV (defined as having had more than one sexual partner in the last	
12 months OR having been treated for an STI and/or BV in the last 12 months)	
No BV by Nugent score or TV by wet mount or culture	
Clinician-observed genital ulcers, condylomata, or other genital abnormalities at the Screening	
visit	
Underwent a gynaecological surgery/invasive procedure in the 3 months prior to screening	
History of significant urogenital prolapse, undiagnosed vaginal bleeding, urine or faecal	
incontinence, or blood clotting disorders	
Allergic to metronidazole or any other components of the study drugs	
Participating in another health intervention study	
Other (each reason will be listed)	
TOTAL number of women	102

At the Enrolment visit	
Enrolment target already met	
Did not adhere to 7-day metronidazole treatment	
BV or TV not adequately treated	
Pregnant at the Enrolment visit	
STI or UTI at the Enrolment visit	
Other (each reason will be listed)	
TOTAL number of women	6

3.4 Numbers of and reasons for unscheduled visits

Time period	Number of women	Number of visits
Between the Screening and Enrolment visits (not including		
Results visits scheduled by RU staff)		
Between Enrolment and M1		
Between M1 and M2		
Between M2 and M6		
After M6		
TOTAL		

Reasons for unscheduled visits	Number of visits
To withdraw informed consent	
To obtain additional study product supplies	
To report an (S)AE or social harm	
To test for an STI or vaginal infection	
To test for a UTI	
To collect treatment for a positive lab result	
Wants to be tested for HIV or pregnancy	
For male partner HIV/STI testing and couple counselling	
To ask questions or express concerns	
Other (each reason will be listed)	
TOTAL	

4. Analyses of baseline data

4.1 Characteristics of the total screened and randomised populations (collected at Screening)

All participants who attended a Screening visit underwent a face-to-face interview, and an HV and pregnancy test. Women who tested positive for HIV or pregnancy did not always undergo a speculum examination or any further diagnostic testing.

Sociodemographics	Screened (N=174)	Randomised (N=68)
Kigali neighbourhood (n/N % per category)		
Age (median, IQR)		
Age, categorised (n/N % per category)		
- 18 to 25		
- 26 to 35		
- 36 to 45		
Marital status (n/N % per category)		

Education level (n/N % per category)		
Sexual history and behaviour	Screened (N=174)	Randomised (N=68)
Number of sex partners in lifetime (median, IQR)		
Number of sex partners last 12 months (median, IQR)		
Number of sex partners last month (median, IQR)		
Currently has a main sex partner (n/N %)		
Lives together with main sex partner (n/N %)		
Main sex partner circumcised (n/N % per category)		
- Yes		
- No		
- Does not know		
Main sex partner has other sex partners (n/N % per		
category)		
- Yes		
- No		
- Does not know		
Vaginal sex frequency last 2 weeks (median, IQR)		
Any condom use in past two weeks (n/N %)		
Condom use during last sex act (n/N %)		
Exchanged sex for money/goods in past month (n/N %)		
Reproductive and contraceptive history	Screened (N=174)	Randomised (N=68)
Pregnancies in lifetime (median, IQR)	Scieelieu (N-174)	
Deliveries in lifetime (median, IQR)		
Miscarriages in lifetime (median, IQR)		
Currently breastfeeding (n/N %)		
Ever severe infection with fever during		
pregnancy/childbirth (n/N %)		
Ever baby with severe infection with fever within days		
after birth (n/N %)		
Currently using a modern method of contraception other		
than condoms (n/N % per category):		
- Pills		
- Injections		
- Implant		
- Copper IUD		
- Sterilised		
- Other (described in footnote)		
Medical history	Screened (N=174)	Randomised (N=68)
Any significant medical and/or surgical history or current		
condition (n/N %; describe in footnote)		
Ever had surgery (n/N %; describe in footnote)		~ ⁺
Any gynaecological surgery / invasive procedure last 3		0*
months (n/N %)		
Any chronic diseases (n/N %; describe in footnote)		
Past or current significant urogenital prolapse (n/N %)		0*
Past or current undiagnosed vaginal bleeding (n/N %)		0*
Past or current urine or faecal incontinence (n/N %)		0*
Past or current blood clotting disorder (n/N %)		0*
Ever had allergic reaction (n/N %)		0*

Ever treated for BV (n/N %)		
Ever treated for vaginal candidiasis (n/N %)		
Treated for STI in the past 12 months (n/N %)		
Current medications and symptoms	Screened (N=174)	Randomised (N=68)
Any current medication use (n/N %; describe in footnote)		
Any urogenital symptoms now or in last 2 weeks, patient-		
reported (n/N%)		
If yes, what symptoms ¹ (n/N % per category):		
 Burning when passing urine 		
 Frequent urination or urgent need to urinate 		
– Blood in urine		
 Genital burning 		
 Genital itching 		
 Pain during sex 		
 Lower abdominal pain 		
 Unusual vaginal discharge 		
 Sores in the genital and/or anal area (including 		
buttocks)		
 Other (additional categories to be added if needed) 		
If yes, already received treatment (n/N %)		
If yes, some or all of the symptoms are currently ongoing		
(n/N %)		
Medical procedures by study physician	Screened (N=174)	Randomised (N=68)
Any abnormal pelvic exam findings (n/N % per category)		
Any abnormal bimanual exam findings (n/N % per		
Any abnormal bimanual exam findings (n/N % per category)		
category) Clinical diagnosis (n/N % per category)		
category) Clinical diagnosis (n/N % per category) Treatment given (n/N % per category)		
category) Clinical diagnosis (n/N % per category) Treatment given (n/N % per category) Laboratory results	Screened (N=174)	Randomised (N=68)
category) Clinical diagnosis (n/N % per category) Treatment given (n/N % per category) Laboratory results HIV serology positive ² (n/N %)	Screened (N=174)	0*
category) Clinical diagnosis (n/N % per category) Treatment given (n/N % per category) Laboratory results HIV serology positive ² (n/N %) Urine pregnancy test positive ³ (n/N %)	Screened (N=174)	0* 0*
category) Clinical diagnosis (n/N % per category) Treatment given (n/N % per category) Laboratory results HIV serology positive ² (n/N %) Urine pregnancy test positive ³ (n/N %) UTI by urinalysis positive ⁴ (n/N %)	Screened (N=174)	0*
category) Clinical diagnosis (n/N % per category) Treatment given (n/N % per category) Laboratory results HIV serology positive ² (n/N %) Urine pregnancy test positive ³ (n/N %)	Screened (N=174)	0* 0*
category) Clinical diagnosis (n/N % per category) Treatment given (n/N % per category) Laboratory results HIV serology positive ² (n/N %) Urine pregnancy test positive ³ (n/N %) UTI by urinalysis positive ⁴ (n/N %) BV by modified Amsel criteria positive ⁵ (n/N %) Nugent 4-10 on Gram stain (n/N %)	Screened (N=174)	0* 0* 0*
category) Clinical diagnosis (n/N % per category) Treatment given (n/N % per category) Laboratory results HIV serology positive ² (n/N %) Urine pregnancy test positive ³ (n/N %) UTI by urinalysis positive ⁴ (n/N %) BV by modified Amsel criteria positive ⁵ (n/N %) Nugent 4-10 on Gram stain (n/N %) Nugent 7-10 on Gram stain (n/N %)	Screened (N=174)	0* 0* 0*
category) Clinical diagnosis (n/N % per category) Treatment given (n/N % per category) Laboratory results HIV serology positive ² (n/N %) Urine pregnancy test positive ³ (n/N %) UTI by urinalysis positive ⁴ (n/N %) BV by modified Amsel criteria positive ⁵ (n/N %) Nugent 4-10 on Gram stain (n/N %) Nugent 7-10 on Gram stain (n/N %) Nugent 4-6 on Gram stain (n/N %)	Screened (N=174)	0* 0* 0* 0*
category) Clinical diagnosis (n/N % per category) Treatment given (n/N % per category) Laboratory results HIV serology positive ² (n/N %) Urine pregnancy test positive ³ (n/N %) UTI by urinalysis positive ⁴ (n/N %) BV by modified Amsel criteria positive ⁵ (n/N %) Nugent 4-10 on Gram stain (n/N %) Nugent 4-6 on Gram stain (n/N %) TV on wet mount (n/N %)	Screened (N=174)	0* 0* 0*
category) Clinical diagnosis (n/N % per category) Treatment given (n/N % per category) Laboratory results HIV serology positive ² (n/N %) Urine pregnancy test positive ³ (n/N %) UTI by urinalysis positive ⁴ (n/N %) BV by modified Amsel criteria positive ⁵ (n/N %) Nugent 4-10 on Gram stain (n/N %) Nugent 7-10 on Gram stain (n/N %) Nugent 4-6 on Gram stain (n/N %) TV on wet mount (n/N %) TV by InPouch culture (n/N %)	Screened (N=174)	0* 0* 0* 0*
category) Clinical diagnosis (n/N % per category) Treatment given (n/N % per category) Laboratory results HIV serology positive ² (n/N %) Urine pregnancy test positive ³ (n/N %) UTI by urinalysis positive ⁴ (n/N %) BV by modified Amsel criteria positive ⁵ (n/N %) Nugent 4-10 on Gram stain (n/N %) Nugent 7-10 on Gram stain (n/N %) Nugent 4-6 on Gram stain (n/N %) TV on wet mount (n/N %) TV by InPouch culture (n/N %) Candida on wet mount (n/N %)	Screened (N=174)	0* 0* 0* 0* 0* 0*
category) Clinical diagnosis (n/N % per category) Treatment given (n/N % per category) Laboratory results HIV serology positive ² (n/N %) Urine pregnancy test positive ³ (n/N %) UTI by urinalysis positive ⁴ (n/N %) BV by modified Amsel criteria positive ⁵ (n/N %) Nugent 4-10 on Gram stain (n/N %) Nugent 7-10 on Gram stain (n/N %) Nugent 4-6 on Gram stain (n/N %) TV on wet mount (n/N %) TV on wet mount (n/N %) TV by InPouch culture (n/N %) Syphilis serology positive ⁶ (n/N %)	Screened (N=174)	0* 0* 0* 0*
category) Clinical diagnosis (n/N % per category) Treatment given (n/N % per category) Laboratory results HIV serology positive ² (n/N %) Urine pregnancy test positive ³ (n/N %) UTI by urinalysis positive ⁴ (n/N %) BV by modified Amsel criteria positive ⁵ (n/N %) Nugent 4-10 on Gram stain (n/N %) Nugent 4-6 on Gram stain (n/N %) Nugent 4-6 on Gram stain (n/N %) TV on wet mount (n/N %) TV on wet mount (n/N %) Candida on wet mount (n/N %) Syphilis serology positive ⁶ (n/N %) HSV-2 serology positive ⁷ (n/N %)	Screened (N=174)	0* 0* 0* 0* 0* 0*
category) Clinical diagnosis (n/N % per category) Treatment given (n/N % per category) Laboratory results HIV serology positive ² (n/N %) Urine pregnancy test positive ³ (n/N %) UTI by urinalysis positive ⁴ (n/N %) BV by modified Amsel criteria positive ⁵ (n/N %) Nugent 4-10 on Gram stain (n/N %) Nugent 7-10 on Gram stain (n/N %) Nugent 4-6 on Gram stain (n/N %) TV on wet mount (n/N %) TV on wet mount (n/N %) TV by InPouch culture (n/N %) Candida on wet mount (n/N %) Syphilis serology positive ⁶ (n/N %) HSV-2 serology positive ⁷ (n/N %) CT PCR positive (n/N %)	Screened (N=174)	0* 0* 0* 0* 0* 0*
category) Clinical diagnosis (n/N % per category) Treatment given (n/N % per category) Laboratory results HIV serology positive ² (n/N %) Urine pregnancy test positive ³ (n/N %) UTI by urinalysis positive ⁴ (n/N %) BV by modified Amsel criteria positive ⁵ (n/N %) Nugent 4-10 on Gram stain (n/N %) Nugent 7-10 on Gram stain (n/N %) Nugent 4-6 on Gram stain (n/N %) TV on wet mount (n/N %) TV on wet mount (n/N %) Candida on wet mount (n/N %) Syphilis serology positive ⁶ (n/N %)	Screened (N=174)	0* 0* 0* 0* 0* 0*

* These were exclusion criteria and can therefore not be present in the randomised population.

1. Percentages can add to more than 100% because participants were allowed to give multiple answers.

2. Kehua HIV Rapid Test (Kehua Bioengineering Co., Shanghai, China) with Determine HIV Rapid Test (Abbott Laboratories, Tokyo, Japan) for confirmation of positive results and the Unigold HIV Rapid Test (Trinity Biotech Plc, Bray, Ireland) as tie-breaker.

3. Nova hCG urine pregnancy test (Nova, Waltham, USA).

4. Nova urinalysis dipstick test (Nova, Waltham, USA), considered UTI-positive if nitrites were positive or at least 1+ leucocytes (in

accordance with Rwandan guidelines).

- 5. The modified Amsel score was positive if 2 or 3 of the following criteria were positive: 1) >20% clue cells on wet mount 2) a positive KOH (amine) test; 3) vaginal pH > 4.5.
- 6. Spinreact *T. pallidum* Haemagglutination test with confirmation of active infection by Spinreact Rapid Plasma Reagin test (Spinreact, Girona, Spain).
- 7. Kalon HSV-2 test (Kalon, Guildford, United Kingdom), with optical density (OD) > 1.1 of the mean OD of the cut-off defined as positive) and < 0.9 of the OD of the cut-off defined as negative.

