5.2 Eligibility criteria

Inclusion criteria:

- Female, 18-45 years old
- Sexually active, defined as having had sex at least twice in the two weeks prior to screening
- At high risk of HIV/STIs/BV, defined as having had more than one sexual partner in the last 12 months OR having been treated for an STI and/or BV in the last 12 months
- Successfully treated for BV by Amsel criteria or TV (defined as no BV by Amsel criteria and no TV on wet mount at the enrolment visit) and free of HIV (at screening), pregnancy (at screening and the enrolment visit), symptomatic vaginal candidiasis and UTI (at the enrolment visit), and syphilis, NG, and CT (at the results visit). Due to the long turn-around time for NG and CT lab test results, women may be enrolled when their NG and CT results are not yet known, but a new participant will be randomised for each woman whose screening sample comes back positive for NG and/or CT after having been randomised. The NG/CT-positive women will be allowed to complete the study but their data may be removed from some analyses.
- Currently in good physical and mental health as judged by a study physician
- Willing and able to adhere to study procedures and provide written informed consent.

According to Rwandan ethics guidelines, unmarried women aged 18-20 also need the written informed consent of a parent or guardian.

 Women are allowed to use contraception, including hormonal contraception; use of these methods will be taken into account in the instructions given to women about probiotic use and in the data analysis.

Exclusion criteria:

- HIV positive
- Pregnant
- Clinician-observed genital ulcers, condylomata, or other genital abnormalities at screening and/or enrolment
- Underwent a gynaecological surgery/invasive procedure in the 3 months prior to screening
- History of significant urogenital prolapse, undiagnosed vaginal bleeding, urine or faecal incontinence, or blood clotting disorders
- Allergic to metronidazole or any other components of the study drugs
- Not willing to stop use of other oral or vaginal probiotics from the screening visit until the end
 of study participation
- Participating in another health intervention study
- For any other reason potentially interfering with participant safety or protocol adherence as judged by the Principal Investigator (these reasons will be recorded)

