4.2 Baseline characteristics per randomisation group (collected at Screening)

For all participants that were enrolled, the same baseline characteristics at Screening will be shown in the following table. The differences between all four study arms will be compared by eyeballing; no formal statistical tests will be performed.

The laboratory results of the enrolled and randomized participants (during the Screening visit) will be reported. Some of the tests were only performed in a subset of participants (for instance, participants were ineligible due to being HIV-positive or pregnant, and were therefore not further tested for STIs such as CT, NG, HSV-2, etc). The laboratory results per enrolled arm will also be reported.

Sociodemographics	Group 1 N=17	Group 2 N=17	Group 3 N=17	Group 4 N=17
Kigali neighbourhood (n % per category) ¹				
Age (median, IQR)				
Age, categorised (n % per category)				
- 18 to 25				
- 26 to 35				
- 36 to 45				
Marital status (n % per category)				
Education level (n % per category)				
Sexual history and behaviour	Group 1	Group 2	Group 3	Group 4
Number of sex partners in lifetime (median, IQR)				
Number of sex partners last 12 months (median, IQR)				
Number of sex partners last month (median, IQR)				
Currently has a main sex partner (n %)				
Lives together with main sex partner (n %)				
Main sex partner circumcised (n % per category)				
- Yes				
- Does not know				
- No				
Main sex partner has other sex partners (n % per category)				
- Yes				
- Does not know				
- No				
Vaginal sex frequency last 2 weeks (median, IQR)				
Any condom use in past two weeks (n %)				
Condom use during last sex act (n %)				
Exchanged sex for money/goods in past month (n %)				
Reproductive and contraceptive history	Group 1	Group 2	Group 3	Group 4
Pregnancies in lifetime (median, IQR)				
Deliveries in lifetime (median, IQR)				
Miscarriages in lifetime (median, IQR)				
Varcian 9 November 2016				11

Currently breastfeeding (n %)				
Ever severe infection with fever during pregnancy/childbirth				
(n %)				
Ever baby with severe infection with fever within days after				
birth (n %)				
Currently using a modern method of contraception other				
than condoms (n % per category): - Pills				
- Injections				
- Implant				
- Copper IUD - Sterilised				
- Other (described in footnote)	Crear 1	C	C	Current A
Medical history	Group 1 N=17	Group 2 N=17	Group 3 N=17	Group 4 N=17
Any significant medical and/or surgical history or current				

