8.1 Incidence and incidence rate ratios of secondary efficacy outcomes

It has been hypothesised that a lactobacilli-dominated VMB would protect women from HIV, other STIs, and UTIs, and would facilitate pregnancy. While the sample size of this study was too small to adequately test these hypotheses, we did include incidence of HIV, STIs (other than TV), UTIs, and pregnancy as secondary outcomes. Women were tested for HIV and STIs (HSV-2, syphilis, CT, and NG) at the Screening and M6 visits, and for UTI and pregnancy at the Screening, Enrolment and M6 visits. In all cases, additional testing may have been done at the D7, M1 and M2 visits when clinically indicated. Incidence of these secondary outcomes will be determined between baseline (using endpoint data from the Enrolment visit if available and otherwise from the Screening visit) and M6.

Incident cases will be defined as follows:

- HIV: a positive result for the HIV serology algorithm at M6. Women who were HIV-positive at Screening were excluded from the study; therefore, all positive results at M6 will be treated as incident cases. Time at risk will start at the Enrolment visit.
- HSV-2: a positive result for HSV-2 serology at M6. Only those participants who tested negative for HSV-2 at Screening were retested at M6; therefore, all positive cases at M6 will be treated as incident cases. Time at risk will start at the Enrolment visit.
- Syphilis: a positive result for the syphilis serology algorithm at M6. All participants positive for syphilis at Screening were adequately treated prior to randomisation; therefore, all positive cases at M6 will be treated as incident cases. Time at risk will start at the Enrolment visit.
- NG: a positive result for NG PCR at M6 after a negative NG PCR result at Screening (time at risk will start at the Enrolment visit) or after having been successfully treated for NG during follow-up (time at risk will start on the treatment completion date).
- CT: a positive result for CT PCR at M6 after a negative CT PCR result at Screening (time at risk will start at the Enrolment visit) or after having been successfully treated for CT during follow-up (time at risk will start on the treatment completion date).

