- UTI: a positive urinalysis result (according to the Rwandan guidelines) at M6 or earlier during follow-up if tested due to symptoms after a negative urinalysis dipstick result at an earlier visit or after adequate UTI treatment. Time at risk will always start at the Enrolment visit because all UTI's at the Screening and Enrolment visits were treated prior to randomisation.
- Pregnancy: a positive urine pregnancy test at M6 (or earlier during follow-up). As being pregnant at Screening or Enrolment was a reason for exclusion in this study, all positive results will be treated as incident cases.

Incidence rates: IRs will be calculated as the number of incident cases per person-days (PD) of follow-up with 95% confidence intervals using the IR function in STATA. IRs will be calculated for each primary endpoint in each of the 4 randomisation groups and for the entire study population. In all cases, IRs will be calculated for the entire follow-up period as described above.

	Group 1		Group 2		Group 3		Group 4		Total	
	n/N ¹	Cases/PD (IR, 95% CI) ²	n/N¹	Cases/PD (IR, 95% CI) ²	n/N¹	Cases/PD (IR, 95% CI) ²	n/N¹	Cases/PD (IR, 95% CI) ²	n/N¹	Cases/PD (IR, 95% CI) ²
HIV										
HSV-2										
Syphilis										
NG										
СТ										
UTI										
Pregnancy										

1. Number of women (n) who developed at least one incident infection during the specified time period as a proportion of the women who completed all follow-up visits in that time period (N).

2. Incident rate (IR): Number of incidence cases per person-days of follow-up, with 95% confidence intervals (CI).

Incidence rate ratios (IRRs) with 95% confidence intervals will be calculated comparing each product use group (groups 2-4) to the control group (group 1) using the IR function in STATA. In addition, IRRs with 95% confidence intervals will be calculated comparing each vaginal probiotic group (group 3 and 4) to the metronidazole group (group 2). As before, these IRRs will be calculated for each primary efficacy outcome for the entire follow-up period.

	Group 2 vs 1 IRR (95% CI)	Group 3 vs 1 IRR (95% CI)	Group 4 vs 1 IRR (95% CI)	Group 3 vs 2 IRR (95% CI)	Group 4 vs 2 IRR (95% CI)
HIV					
HSV-2					
Syphilis					
NG					
СТ					
UTI					
Pregnancy					

The number of incident infections will likely be too small to allow for per-protocol analyses and GEE models as described for the primary efficacy outcomes in 6.3 and 6.4.

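### SAP table 4.1 pre-fills zeros for randomised women on Screening rows that were not exclusions at Screening (minor)

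*SAP*

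**What the plan says.** The heading of SAP 4.1 states that the characteristics were collected at Screening, that is, before the metronidazole course and before enrolment. In the column for the 68 randomised women some cells already hold 0*, explained by the footnote "These were exclusion criteria and can therefore not be present in the randomised population".

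Six medical-history rows are legibly marked: recent gynaecological procedure, prolapse, undiagnosed bleeding, incontinence, clotting disorder, and the row beginning "Ever had allergic reaction (n/N". The laboratory block also carries 0* marks, up to six of them, but its layout is broken in the available text.

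SAP 4.2 then introduces the by-arm table: "For all participants that were enrolled, the same baseline characteristics at Screening will be shown in the following table". Its shell nevertheless leaves out the six marked medical-history rows and six laboratory rows: HIV, pregnancy, UTI, modified Amsel BV, TV on wet mount and syphilis.

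**The concern.** A pre-filled zero is safe only if the condition, at the visit the table describes, made a woman ineligible. Several marked rows appear to be conditions that a woman could have at Screening and still be randomised after treatment. One row is defined more widely than the exclusion it stands for.

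Three things are at stake:

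- **Description of the population.** The Screened column sits beside the Randomised column. Observed Amsel BV and wet-mount TV among screened women next to a fixed zero among randomised women would suggest that the trial selected women without them.
- **Comparison of arms.** SAP 6.4 allows one or two extra covariates if variables in 4.2 or 4.3 look imbalanced. A row that is not shown by arm cannot be seen to be imbalanced. Incident BV by modified Amsel criteria is a primary efficacy outcome, so its Screening distribution is of interest.
- **Syphilis incidence.** SAP 8.1 counts every positive at Month 6 as incident because Screening positives had been treated. A fixed zero at Screening hides how many women that reasoning covers.

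**Working it through.** No sample-size or power formula applies. The check compares each pre-filled zero with the eligibility rules.

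**Step 1: which rows carry 0\*.** In the medical-history block the six marked rows are legible, and they are exactly the six that 4.2 drops. Applying the same rule to the laboratory block, the 4.1 rows missing from 4.2 are HIV, pregnancy, UTI, modified Amsel BV, TV on wet mount and syphilis. That is six rows, equal to the largest number of 0* marks visible in the block. This mapping is an inference.

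**Step 2: was each condition an exclusion at Screening?**

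| Row in 4.1 | What the documents say | Zero guaranteed at Screening? |
|---|---|---|
| HIV, pregnancy | Not eligible if positive at Screening (Protocol 5.2, 6.2) | Yes |
| Gynaecological procedure, prolapse, undiagnosed bleeding, incontinence, clotting disorder | Listed exclusions (Protocol 5.2) | Yes |
| Any past allergic reaction | The exclusion is narrower: "Allergic to metronidazole or any other components of the study drugs" (Protocol 5.2; same item in SAP 3.3) | No |
| Modified Amsel BV | Protocol entry condition: "Successfully treated for BV by Amsel criteria or TV", with absence required at the enrolment visit. SAP 1.1 enters BV by Nugent, and Amsel positivity is no bar | No |
| TV on wet mount | Entry route in Protocol 6.2 and SAP 1.1. SAP 3.3 lists the lack of BV and TV as the reason for ineligibility | No |
| UTI | Treated at Screening, while HIV and pregnancy are referred (Protocol 6.2). SAP 8.1: "all UTI's at the Screening and Enrolment visits were treated prior to randomisation" | No |
| Syphilis | Treated, then a repeat wet mount and a route to enrolment (Protocol 6.3). SAP 8.1: "All participants positive for syphilis at Screening were adequately treated prior to randomisation" | No |

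Count: 6 medical-history zeros + 6 laboratory zeros = 12. Supported: 5 + 2 = 7. Unsupported: 1 + 4 = 5.

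**Step 3: does the count depend on the mapping?** If the block holds six zeros and only two laboratory conditions excluded at Screening, then 6 − 2 = 4 zeros are misplaced, whichever rows they occupy. This still relies on the count of six. The allergy row relies on neither.

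**Step 4: what zeros for both Amsel BV and wet-mount TV would imply.** Set aside women who qualified on a repeat wet mount. Under the protocol's entry rule, all 68 would then have entered on TV culture alone. Under the SAP's rule, all 68 would have had either Nugent BV that was Amsel-negative or TV found only by culture. SAP 6.3 speaks of women who no longer met the modified Amsel criteria at Enrolment, which implies that some had met them before.

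**Step 5: illustration.** The documents do not give the proportion of randomised women who were Amsel-positive at Screening, so p below is assumed, with women taken as independent. Expected count = 68p; chance of a true zero = (1 − p)^68.

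- p = 0.05: 3.4 expected, chance 0.031
- p = 0.10: 6.8 expected, chance 0.0008
- p = 0.30: 20.4 expected, chance 3 × 10⁻¹¹

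**The case against.** **The laboratory mapping rests on damaged text.** This stands as a limit. The block is repeated in fragments with different numbers of 0* marks, so position alone cannot tie a zero to a row. The exact match with the rows dropped from 4.2, in both blocks, makes the mapping well supported but not certain.

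**The zeros may describe status at randomisation.** Protocol 5.2 requires no Amsel BV, wet-mount TV or UTI at the enrolment visit, and no syphilis at the results visit. Read that way, the laboratory zeros would be right and the time-point label wrong. Syphilis is the closest case, because the results visit reports the Screening blood sample; but Protocol 6.3 and SAP 8.1 both treat a Screening positive as treatable and still enrollable. The table says Screening, so the label and the cells disagree either way. This reading does not rescue the allergy row.

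**The text of 4.2 promises Screening laboratory results for randomised women and by arm.** It does, but the shell lacks the rows. SAP section 5 tabulates Amsel and wet-mount results over all visits, not by arm.

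**Stronger readings.** A reader might infer that the qualifying diagnosis vanishes from the by-arm table. It does not: 4.2 keeps Nugent 4-10, 7-10 and 4-6 and TV culture, and Nugent is both the SAP's BV entry diagnosis (1.1, 3.3) and the outcome of the GEE models (6.4). A reader might also infer that allergy was not an exclusion at all. It was, for metronidazole and study-drug components, and the counts in SAP 3.3 are blank.

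**Conclusion.** Wrong as written; minor severity. The allergy row is a clear error. Four laboratory rows (modified Amsel BV, TV on wet mount, UTI, syphilis) are very probably wrong too, on the assumption that the rows dropped from 4.2 are those marked 0* in 4.1. That makes 5 of 12 pre-filled zeros unsupported for the 68 randomised women. Each is false if even one randomised woman had the condition at Screening. For Amsel BV and wet-mount TV together a true zero is hard to reconcile with the entry rules; for UTI, syphilis and allergy the true count is simply unknown.

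The consequence is a misleading baseline description and five rows that cannot be inspected by arm when covariates are chosen under 6.4. It would go too far to infer that efficacy results are affected: primary incidence rates, rate ratios and GEE outcomes use none of these cells.

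**What to change.** - In 4.1, keep 0* only for HIV, pregnancy, recent gynaecological procedure, prolapse, undiagnosed bleeding, incontinence and clotting disorder.
- Report observed Screening n/N among randomised women for modified Amsel BV, TV on wet mount, UTI, syphilis and any past allergic reaction.
- Add these five rows by arm in 4.2, so that the shell matches its introductory sentence.
- If the zeros were meant as status at Enrolment, show them in a separate column labelled Enrolment.
- Check the laboratory rows against the intact SAP table first, since the mapping here is inferred.

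The cost is an edit to two table shells using data already collected. No analysis changes.
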